During the pre-intervention assessment, participants will complete clinical, neuropsychological, and interoception measures as well as EEG, psychophysiology, and fMRI. This session will last approximately 60 minutes and the participant will be compensated \$50. Visits 2-5 will involve breath-focused meditation for both augmented and non-augmented groups and concurrent measurements of EEG and psychophysiology. During visits 6-7, the non-augmented group will continue breath-focused meditation, whereas the augmented group will receive tapering levels of feedback, such that no physiological feedback will be present by the end of each session. Visit 8 will require the participant to complete the same tasks and surveys

completed during the first visit, as well as the MRI scan. These intervention visits will last 50 minutes each and the participant will be compensated \$20 per session for up to 7 sessions. The one-month follow-up will include only relevant self-report measures. This session will last approximately 60 minutes and the participant will be reimbursed \$50. Finally, the second follow up visit will last approximately 2 hours; this session will include 2 computer tasks completed inside the MRI scanner and self-report questionnaires. Compensation in the amount of \$50 will be provided for this follow-up.

Google Voice texting, a free texting service will be used to assist in study retention. Participants can miss intervention sessions due to forgetting their appointment times and missing reminder calls. The use of this texting service will allow participants to receive text message reminders of their appointments in addition the reminder calls.

Reimbursement to participants will be given via e-gift card. Participants will be emailed the e-gift card following each visit. E-gift cards will be purchased through Emory Express.

Measures:

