Data from this study will be based on self-report measures and behavioral tasks to be completed by participants. The self-report measures include the *Multiscale Dissociation Inventory* (MDI; Briere et al. 2005), the *Clinician Administered PTSD Scale* (CAPS) and *PTSD symptom Scale* (PSS), the *Kentucky Mindfulness Scale* (KIMS), the *Multidimensional Assessment of Interoceptive Awareness* (MAIA), and the *Kreek-McHugh-Schluger-Kellogg scale* (KMSK). The behavioral tasks include the breath focus task, rumination task, Affective Number Stroop task, Penn Computerized Neuropsychological Battery (Penn CNP). All self-report measures as well as the behavioral tasks will be administered during the pre- and post-interventions and the one-month follow-up session. During the last follow-up session, we will administer Affective Number Stroop and Visual Statistical Learning behavioral tasks as well as *Barriers to Needs Questionnaire* (BTNQ) self-report measure.

MDI. The MDI is a 30-item self-report test of dissociative symptomology and it measures six different types of dissociative response. The scales of the MDI are disengagement, depersonalization, derealization, emotional constriction/numbing, memory disturbance, identity dissociation, and total dissociation.

CAPS. The CAPS is a 30-item structured interview that can be used to make current and lifetime diagnosis of PTSD as well as assess PTSD symptoms over the past week. Questions also examine the onset and duration of symptoms, subjective distress, impact of symptoms on social and occupational functioning, improvement in symptoms since a previous CAPS administration, overall response validity, overall PTSD severity, and specifications for the dissociative subtype (depersonalization and derealization). The identification of an index traumatic event to serves as the basis for symptom inquiry. The full interview takes approximately 45-60 minutes to administer.

MINI Neuropsychiatric Interview is a semi-structured interview that will be used to assess for concurrent mood, substance, and psychotic disorders ([Sheehan et al., 1998](#)). The interview takes 30 minutes - 1 hour to administer.

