We have designed this study to have a final sample of 80 participants. The sample size of 80 was determined using a power analysis. Power was calculated using theoretical maximum detectable effect sizes given our samples. The proposed design, involving 40 completers in the active intervention arm and 40 completers in the control arm will yield sufficient power to detect effects at $d > .5$ for Aim 1) effects of the intervention of $d > .6$ and Aims 2 and 3) change in mechanism within the active group ($d > .6$) and across groups ($d > .6$). Although 80 is the minimum number needed to achieve statistically significant effects for our conditions of interest, we will enroll a higher number (110) with the expectation of attrition for some of these individuals.

All electronic data will be secured via an Emory secure network and password protection. Data will be managed electronically using REDcap. All participant data will be de-identified and all participants will be given a subject ID. Data gathered at each session will then be entered into REDcap with previous data and a hard copy of all data will be saved in a participant's folder. All hard copy data will be secured by storing it in a de-identified folder in a locked office in a locked

filing cabinet. Documentation regarding each session will also be kept as a hard copy in a participant's folder after being signed by both study researcher and licensed supervisor.

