Statistical analyses will not be conducted until the conclusion of the study when all measures and data have been collected. Analyses of behavioral data will be conducted using SPSS software. For analyses of fMRI activity, first-level, fixed-effect models will be created for each participant based on responses to each event of interest, which will be convolved with the hemodynamic response function. Events of interest include: breath-focus vs no breath focus; number congruent/number incongruent; error/missed responses. Motion regressors will be included in first-level models. Functional connectivity analyses will be conducted for affective challenge conditions including the incongruent trials from the Affective Number Stroop and rumination condition on the Rumination task. Within these conditions we will examine global connectivity indices (correlation of every voxel with every other voxel above and beyond physiological artifacts including respiration) within the proposed interoceptive network. These correlations will be transformed into standardized (z') indices for which the mean will be preserved per participant for group-level analyses.

Group (augmented vs non-augmented breath-focus mindfulness) by time (pre-post) mixed-effects analyses will be conducted on voxel-wise activity and mean global connectivity in the interoceptive network to examine intervention-related differences ($p < .05_{\text{corrected}}$). Functional relationships between different brain regions acquired over time, e.g., different brain regions, before and after intervention will be examined using Bayesian Belief networks (BNs). Mixed effects analysis [group x time (pre/post/follow-up)] will be used to examine clinical effects in 1) PTSD symptoms, measured by the CAPS (at 1 month) and PSS (immediately post-treatment); 2) Dissociative symptoms, measured by the MDI; 3) Mindfulness skills, measured by the Kentucky Mindfulness Scale.

Training:

All research assistants will be trained in all measures being used in the study and will fully understand the goals and purpose of the research proposed. These research personnel will be under the supervision of [name].

Data Management and Monitoring:

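### The group x time tests, as ordinarily read, leave the arms' baseline means free; if arms are randomised and baseline and later SDs are similar, baseline adjustment gains power at low to moderate pre-post correlation

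*Combined protocol and SAP*

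**What the plan says.** The Data Analysis section describes two families of model.

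- Clinical outcomes (PTSD symptoms, MDI, Kentucky Mindfulness Scale): "Mixed effects analysis [group x time (pre/post/follow-up)] will be used to examine clinical effects in 1) PTSD symptoms".
- Imaging: "Group (augmented vs non-augmented breath-focus mindfulness) by time (pre-post) mixed-effects analyses will be conducted on voxel-wise activity and mean global connectivity".

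In both, the pre-treatment value is a level of time. No model equation, baseline covariate, common baseline mean or covariance structure is given.

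The same section ties the PTSD measures to one later time each ("PTSD symptoms, measured by the CAPS (at 1 month) and PSS (immediately post-treatment"). The Measures section lists the CAPS among the self-report measures and says: "All self-report measures as well as the behavioral tasks will be administered during the pre- and post-interventions and the one-month follow-up session". The Procedure section says of the one-month visit: "The one-month follow-up will include only relevant self-report measures".

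The sample size text plans a comparison "involving 40 completers in the active intervention arm and 40 completers in the control arm", with effects of .5 and .6 both attached to Aim 1 and .6 to Aims 2 and 3. It calls the power sufficient, but gives no power level, significance level, pre-post correlation or SD scale for d. It enrols 110 to reach 80 completers.

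Assignment to arms is not described. Under Recruitment, random selection refers only to whom staff approach in waiting rooms. Entry requires an MDI depersonalization score of 7 and at least two of four CAPS criteria.

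**The concern.** When each arm has its own free baseline mean, the group by time term for one later visit is a two-sample comparison of change scores. Subtracting the whole baseline value adds noise unless baseline predicts the later score closely. Under random assignment the arms have the same expected baseline, and using that fact removes the excess noise. Keeping baseline as a response is not itself the loss; leaving its arm means unconstrained is.

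The baseline values are already collected: "Visit 8 will require the participant to complete the same tasks and surveys" as at the first visit. With 80 completers described as the minimum, an effect of the planned size could be missed more often than the same data require.

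**Working it through.** **Inputs.** From the document: 40 completers per arm; d of .5 and .6. Assumed, because not stated: two-sided 5%, d in outcome SDs, random assignment, r from .3 to .8, equal SDs at first.

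**The plan's own figure.** No numeric power is stated, so none can be reproduced. A plain two-sample t test with 40 per arm has 75.5% power at d=.6 and 59.8% at d=.5; the smallest d with 80% power is about .63.

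**One later visit.** In units of the outcome variance, the planned test has variance factor 2(1−r) with 78 df, and the adjusted test 1−r² with 77 df. Their ratio, adjusted to planned, is (1+r)/2. The noncentrality is d√(20/v). At d=.6, r=.3:

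- planned: v = 1.4, .6√(20/1.4) = 2.27, power 61.0%
- adjusted: v = .91, .6√(20/.91) = 2.81, power 79.3%

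| r | v planned | v adjusted | d=.6, planned v adjusted | d=.5, planned v adjusted |
|---|---|---|---|---|
| .3 | 1.40 | .91 | 61.0 v 79.3% | 46.3 v 63.9% |
| .5 | 1.00 | .75 | 75.5 v 86.4% | 59.8 v 72.2% |
| .7 | .60 | .51 | 92.8 v 96.0% | 81.4 v 87.1% |
| .8 | .40 | .36 | 98.7 v 99.3% | 93.7 v 95.7% |

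**Unequal SDs.** With k = baseline SD / later SD, the planned factor becomes 1+k²−2rk; the adjusted factor stays 1−r². At d=.6, r=.5 (adjusted 86.4% throughout):

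| k | v planned | Planned power | Gain, points |
|---|---|---|---|
| 1.0 | 1.00 | 75.5% | 11 |
| .8 | .84 | 82.4% | 4 |
| .7 | .79 | 84.7% | 2 |
| .6 | .76 | 86.0% | 0.4 |

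At k=.8, r=.3 the figures are 69 v 79%. When r = k the two factors are equal and estimating the slope costs a little: simulation at r=k=.8, d=.3 gives 59.9 v 59.3%, a loss of about 0.6 point.

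**Two later visits, 2-df joint test.** The noncentrality is 20·e′V⁻¹e, where e holds the two effects. At r=.5 with effects .6 and .6:

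- planned: V is the covariance of the two changes (variance 1, covariance .5), so 20 × .72/1.5 = 9.6, power 79.0%
- adjusted: V is the covariance given baseline (variance .75, covariance .25), so 20 × .72/1.0 = 14.4, power 93.0%

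These use 156 and 155 error df; with 77 and 76 they are 78.2 v 92.5%. With unequal correlations .5 (pre-post), .4 (pre-follow-up) and .7 (post-follow-up), and 77 and 76 df, the same effects give 68 v 84%.

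**Type I error of the planned test.** For one later visit it is 5%. For three visits with unstructured covariance it is also about 5%. If equal correlations are imposed while the truth is .5/.4/.7, the 156-df test rejects about 5.6 to 5.7% of the time.

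**If arms are not randomised.** Adjustment leaves a bias of (1−r) times the baseline difference. With a stable 0.3 SD difference, r=.5 and no effect, that is .5 × .3 = .15 SD. The false-positive rate is about 12%, against 5% for the planned test.

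**The case against.** The best case against is that the benefit depends on facts the document does not supply. Random assignment is not stated, and without it the change can do harm. No r is given, and the gain is largest at the low end of the range shown. Selection on MDI depersonalization and CAPS may narrow the baseline SD of exactly those outcomes, which removes much of the gain. The one-line model description does not rule out a common baseline mean. And d may be meant in change-score SDs, since Aims 2 and 3 speak of change in mechanism.

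All of this limits the claim, and none of it removes it. On the change-score scale, planned power at d=.6 is 75.5% at every r, and adjusted power is 91, 86, 82 and 80% at r=.3, .5, .7 and .8, so a gain remains. If a common baseline mean was intended, one sentence would settle it.

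A reader might infer more than the document supports:

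- That the planned analysis is biased or invalid. It is a conventional test, and under random assignment it is valid for one later visit, and for three visits if the covariance is unstructured. The slight excess above arises only under an equal-correlation model, and the document specifies no covariance.
- That the trial is underpowered. Without r, the power target or the scale of d, that cannot be concluded; at r=.7 the planned one-visit test exceeds 80% even at d=.5.
- That the arms are not randomised. The document is silent, which is not evidence either way.

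**Conclusion.** The point holds as a conditional efficiency improvement. For one later visit with similar SDs, adjustment adds 18 points of power at r=.3 and 11 at r=.5 when d=.6, but only about 3 at r=.7 and under 1 at r=.8. It rests on random assignment, the ordinary reading of the group by time model, and assumed values of r and the SD ratio. A narrower baseline SD reduces the gain, in the worst case to a loss of about 0.6 point. Mean connectivity is tested at a corrected threshold, so both of its powers would be lower than those tabulated. The two-visit figures apply to MDI and the Kentucky scale, and to CAPS and PSS only if both later visits are analysed.

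**What to change.** 1. State how participants are assigned to arms. If not at random, do not make this change on this argument.
2. If at random, adjust MDI, Kentucky scale, PSS, CAPS and mean connectivity for the baseline of the same measure. The preferred form is a common baseline mean across arms with unstructured covariance, which keeps participants whose baseline is missing. The alternative, a baseline covariate with its own slope at each visit, drops them.
3. Keep the planned visits. Where there are two later visits, keep a 2-df joint test of the arm differences at post and follow-up. If baseline becomes a covariate, do not test only the remaining group by time term: it compares post with follow-up and has 5% power for equal effects of .6. Do not substitute an averaged contrast: at r=.5 with an effect of .6 at one visit only, it has 47% power against 79% for the planned test.
4. Report the adjusted difference with its interval at each later visit analysed.
5. Reconcile the Measures and Data Analysis sections on the CAPS and PSS visits.

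The voxel-wise maps are outside this proposal. The cost is plan wording and model syntax, with no added participants, visits or measures. The downside is little return if r is about .7 or higher, or if the baseline SD is much smaller than the later SD.

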Research Study Title: Physiological Augmentation of Mindfulness Meditation (PAMM)

Principal Investigators: [name]

Protocol Date: 10/29/2021

NCT Number: NCT02754557

Scientific Protocol

Research Study: Physiological Augmentation of Mindfulness Meditation (PAMM)

Principal Investigators: [name]

Date: 10/29/2021

Background

Specific Aims:

The purpose of the present study is to test the efficacy of implementing breath-focused mindfulness-based interventions (MBIs) to reduce symptoms of dissociation that are associated with posttraumatic stress disorder (PTSD). We will test this intervention in a low-income sample by training increased attention to physiological sensations and basic emotion regulation skills. Additionally, we are interested in whether attentional control can be enhanced in this population via physiological feedback. We propose to evaluate the effectiveness of a breath-focused mindfulness meditation augmented with physiological feedback. This feedback will be given via a vibrating device that will be placed on a participant's sternum that vibrates in proportion to their breathing. Because we are interested in how attention and emotion regulation skills may change as a result of treatment in a real-world setting, such as outpatient clinics of public hospitals, we propose minimal exclusionary criteria and flexible treatment plans.

Supporting Research:

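### Four clinical scales are tested in parallel with no primary outcome and no multiplicity rule; on stated assumptions, the chance of at least one false clinical finding is about 9% to 19% rather than 5%

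*Combined protocol and SAP*

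**What the plan says.** The clinical analysis is a single sentence in the Data Analysis section: "Mixed effects analysis [group x time (pre/post/follow-up)] will be used to examine clinical effects in 1) PTSD symptoms". PTSD symptoms are to be "measured by the CAPS (at 1 month) and PSS (immediately post-treatment"; the list continues with "Dissociative symptoms, measured by the MDI; 3) Mindfulness skills, measured by the Kentucky Mindfulness Scale". That makes three numbered domains and four instruments.

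For these tests the section gives no significance level, no order of testing and no adjustment. The sentence on voxel-wise activity and connectivity, by contrast, sets a corrected .05 threshold.

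Other sections bear on priority without settling it:

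- Specific Aims gives the purpose of the intervention as "to reduce symptoms of dissociation that are associated with posttraumatic stress disorder (PTSD".
- Measures says of the MDI that "it measures six different types of dissociative response", and its list of scales adds a total score. Data Analysis does not say which score is tested.
- Inclusion/Exclusion uses the MDI depersonalization score for eligibility.
- Benefits to Subjects describes possible benefit as a fall in PTSD symptoms, dissociation symptoms, or both.
- The sample size paragraph plans for "40 completers in the active intervention arm and 40 completers in the control arm" but ties its effect sizes to no outcome measure, alpha or power level.

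**The concern.** With several parallel tests and no rule linking them, the 5% error rate applies to each test separately. It does not apply to the statement most readers will take from the trial, namely that augmented meditation does or does not produce a clinical benefit.

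The document also leaves open which result carries the conclusion. Four instruments, seven MDI scores (six scales and a total) and two post-baseline occasions are available. Further scales described under Measures, such as the MAIA, DERS, ACS, CSES and MAP-SR, have no stated role in the analysis. With 40 completers per arm, a chance result on one of these could be reported as a clinical effect, and nothing in this document would mark it as one of many.

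**Working it through.** The document states no family-wise error rate, so there is no figure of its own to reproduce.

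**Inputs from the document**
- Number of tests: k = 4 (CAPS, PSS, MDI, Kentucky), one group by time test each.
- Alternative count: k = 3, if CAPS and PSS, which share the first numbered domain, yield a single PTSD test.

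**Inputs assumed, because the document gives none**
- Two-sided .05 for each clinical test.
- No true effect on any scale (global null).
- A common correlation ρ between the test statistics, varied from 0 to .9.

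**Independent tests.** Family-wise error = 1 − (1 − .05)^k.
- k = 4: 1 − .95^4 = 1 − .8145 = 18.5%.
- k = 3: 1 − .95^3 = 1 − .8574 = 14.3%.

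**Correlated tests.** Write each statistic as Z_i = √ρ·U + √(1 − ρ)·E_i, with U and E_i independent standard normal. The family-wise error is then 1 − E[{Φ((1.96 − √ρ·U)/√(1 − ρ)) − Φ((−1.96 − √ρ·U)/√(1 − ρ))}^k], where the expectation is over U. Numerical integration gives:

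| ρ | k = 4 | k = 3 |
|---|---|---|
| 0 | 18.5% | 14.3% |
| .5 | 15.6% | 12.5% |
| .7 | 13.0% | 10.9% |
| .8 | 11.4% | 9.8% |
| .9 | 9.4% | 8.4% |

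Simulation with 2,000,000 draws per setting agrees to within about 0.1 percentage point.

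**Ratio to nominal, k = 4.** 18.5/5 = 3.7 and 13.0/5 = 2.6; at ρ = .9, 9.4/5 = 1.9. The inflation is therefore about 2 to 3.7 times.

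**Sensitivity**
- With three occasions, the group by time interaction has 2 degrees of freedom. Simulating four such tests gives 18.5% at ρ = 0 and 13.3% at ρ = .7, so the form of the test hardly matters.
- A less uniform pattern (CAPS with PSS .7, MDI with both .5, Kentucky with each of the others −.3) gives 15.9%.
- Sample size does not enter: these are error rates under the null.

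**The case against.** The best defence is that the purpose statement already makes dissociation the target, so the MDI is primary in substance. Part of this stands: the purpose is a sound basis for choosing the primary. But a purpose statement does not fix a score, a time point or an alpha, and Data Analysis gives the MDI no precedence. PTSD being listed first is not a hierarchy either.

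A second defence is that the domains answer separate questions: a Kentucky result speaks to mindfulness skills, not to PTSD or dissociation. This also has force. A reader might infer that, under the plan, success on any one scale establishes efficacy. The document states no such rule; it says only that clinical effects will be examined. The family-wise rate describes what happens if the four results are read together as evidence of clinical benefit.

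Three other stronger readings go beyond the documents:

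- **Eight tests.** A reader might count two post-baseline contrasts for each of four scales. The analysis sentence ties CAPS to one month and PSS to post-treatment, so separate contrasts would number at most six: 1 − .95^6 = 26.5% if independent, and 20.7% at ρ = .5 by the same integration. Even six assumes that the MDI and Kentucky interactions are split by occasion, which the plan does not say.
- **Free choice of outcome after the data are seen.** The document carries a trial registration number, and the registered outcomes are not visible here. The supportable statement is that this document does not fix the choice.
- **A loss of planned power.** Any detectable effect at a given alpha would be the reader's own calculation. The sample size paragraph mentions d > .5 and d > .6 without alpha, power or measure, so no such value can be attributed to the plan.

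**Conclusion.** The concern holds. The document plans parallel tests on four clinical scales and names no primary outcome, score or time point and no multiplicity control for them.

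For four tests, the chance of at least one false clinical finding runs from 18.5% (independent) to 9.4% (ρ = .9). Counting CAPS and PSS as one test gives 14.3% to 8.4%. These figures rest on two-sided .05 per test, no effect on any scale, and assumed correlations. They are illustrations of size, not properties stated in the plan. The direction does not depend on those choices: no combination tried brings the rate down to 5%.

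This should be corrected, but it does not undermine the design. Data Analysis says that analysis waits until all data are collected, so on the document's own timetable the hierarchy can be set beforehand.

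**What to change.** Before any analysis by arm, add the following to Data Analysis:

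1. **Primary.** The group by time contrast from pre-intervention to Visit 8 on one pre-specified MDI score, at two-sided .05. Either the total score or the depersonalization score can be justified: the first matches the general aim of reducing dissociation, the second is the score used for eligibility. The plan must name one.
2. **Secondary.** CAPS at one month, PSS post-treatment and Kentucky at a named time point, with Holm adjustment, tested only if the primary is significant.
3. **Exploratory.** All other scales, MDI scores and time points, labelled as such.

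The gate in step 2 matters. Without it, a primary at .05 plus Holm over three secondaries leaves a chance of any false finding of 1 − .95 × (1 − .05/3)^3 = 9.7% if independent, and about 8.5% at ρ = .5. With the gate, no secondary can be claimed unless the primary is, and the overall error stays at 5%.

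The cost is wording. The primary keeps the full .05. The smallest of the three secondary p-values must fall to .05/3 = .0167 or below, and no secondary can be claimed if the primary fails. If the registered record already names a primary outcome, the text should be reconciled with it.
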